10.5.4 Adverse Events with Onset after End of Trial

If the Investigator becomes aware of an SAE after End of Trial with a suspected causal relationship to the IMPs, it should immediately be reported to Sponsor (see contact details in Section 10.7.1)

10.5.5 Recording of Adverse Events

All events meeting the definition of an AE must be collected and reported in the eCRF. SAEs, and AESIs (whether serious or non-serious) should be reported both in the eCRF and on the Clinical AE Report form.

During each contact with the trial site staff, the patient must be asked about AEs, for example by asking: “Have you experienced any problems since the last contact?” All AEs, observed by the Investigator or patient, must be reported by the Investigator.

10.5.6 Diagnosis of Adverse Events

The Investigator should report the diagnosis, if available. If no diagnosis is available, the Investigator should record each sign and symptom as individual AEs using separate AE forms. If a diagnosis becomes available, the signs and/or symptoms reported should be replaced by the diagnosis.

10.5.7 Onset Date and Time

Start date for an (S)AE is the date of occurrence of the first symptom. The time should be entered if

- the event starts on an IMP dosing day *or* the day after a naxitamab dosing day
- if the duration of the event is less than 24 hours.

10.5.8 End Date and Time

The end date should be filled in if the outcome of an AE is fatal, recovered/resolved or recovered/resolved with sequelae. The end time should be entered for all AEs for which start time should be entered (see section 10.5.7), and/or if the duration of the event is less than 24 hours or if deemed relevant.

10.5.9 Severity

The Investigator will use the CTCAE version 5.0 to describe the severity of the AE. If the severity changes over the course of the event, the grade assigned by the Investigator should be the most severe, that occurred during the AE period.

10.5.10 Outcome

Investigator must judge outcome of the AE by the following terms:

- Recovered
- Recovered with sequelae (description of the sequelae should be provided)
- Not recovered
- Fatal

- Unknown*

*Should only be used if patient is lost to follow-up.

10.5.11 Relationship to Investigational Medicinal Product

The Investigator must assess whether the event is related to the IMPs. A suspected adverse drug reaction is defined as one in which there is a reasonable possibility that one of the IMPs caused the AE. Relatedness must be assessed and reported from the first time the AE is being reported. When assessing the causal relationship of an AE to the IMPs, the following should be taken into consideration:

Not related (unlikely)

The AE is not related to any of the IMPs, which means the AE:

- Does not follow a reasonable temporal sequence from IMP administration
- Is readily explained by the patient's clinical state or by other modes of therapy administered to the patient
- Is clearly not related to the IMP

Possibly Related

The AE follows a reasonable temporal sequence from IMP administration but could have been produced by the patient's clinical state, medical history, or the trial procedures/conditions.

Alternative etiology should be provided for all AEs assessed as possibly related to IMPs.

Probably Related

The AE is probably related to one or more of the IMPs, which means the AE:

- Follows a reasonable temporal sequence from IMP administration
- Abates spontaneously upon discontinuation of the relevant IMP(s) (de-challenge) without any curative treatment
- Is confirmed by reappearance of the same reaction on repeat exposure (re-challenge) (if applicable)
- Cannot be reasonably explained by the known characteristics of the patient's clinical state or medical history

10.5.12 Action Taken with Investigational Medicinal Product

The action taken with the IMPs should be noted as:

- Dose decreased
- Dose administration rate decreased
- Drug interrupted
- Drug postponed

- Drug discontinued
- None
- Not Applicable**
- Unknown.

**: should be used if the AE occurs before first treatment or after end of treatment.

10.6 Events Requiring Immediate Reporting

The following events require reporting within 24 hours of knowledge (for details see Section [10.5](#)):

- SAE
- AESI
- Pregnancy

10.6.1 Pregnancy

Any pregnancy, including partner pregnancy, that occurs during trial participation must be reported to Sponsor within 24 hours of knowledge using the pregnancy form. Pregnant trial patients must be discontinued from IMP treatment immediately (see Section [7.12](#)). The pregnancy must be followed up to determine outcome and status of mother and child. The child must be followed at least to the age of one month. Pregnancy complications and elective terminations for medical reasons must be reported as an AE or SAE. Spontaneous abortions must be reported as an SAE.

10.7 Timelines for Initial Reporting of AEs

SAEs/AESIs

- The paper Clinical AE Report form must be reported from site to Sponsor within 24 hours of the Investigator's first knowledge of the event. The paper Clinical AE Report form is to be sent to the designated drug safety provider (see Section [10.7.1](#)). New follow-up information available at site must be reported within 24 hours of knowledge

All AEs

- The eCRF AE form should be updated in accordance with agreed data entry timelines (see Section [15.2.2](#)).

Please follow the eCRF completion instructions for reporting of AEs.

10.7.1 Contact details for reporting:

Completed paper Clinical AE Report forms and paper pregnancy forms must immediately be reported to:

[contact]

10.8 Follow-up on Adverse Events

SAE/AESIs:

- New follow-up information available at site must be reported within 24 hours of knowledge.
- Follow-up information requested from Sponsor must be replied to within three working days. The eCRF AE form should be updated in accordance to agreed data entry timelines (see Section 15.2.2).
- If an ongoing SAE/AESI changes in intensity, relationship to IMP or as new information becomes available for the event, the paper Clinical AE Report Form should be completed and sent to the designated drug safety provider within 24 hours of the change in assessment (see Section 10.6).
- Grade 3 or higher non-serious AEs that are considered treatment related and all SAEs (including AESIs) should be followed on a regular basis, according to the Investigator's clinical judgment, until the event has been resolved or until the Investigator can assess it as chronic or stable. This includes follow-up after EOT

Non-SAEs

Non-serious AEs should be followed until they are either resolved, returned to baseline, or until 42 days after last dose of IMPs, whichever comes first

10.9 Reporting of SUSARs

Sponsor will ensure that all relevant information about Suspected Unexpected Serious Adverse Reactions (SUSARs) is reported to regulatory authorities in accordance with regulatory requirements.

The Contract Research Organization (CRO) appointed by Sponsor will notify Investigators of SUSARs in accordance with local requirements. Furthermore, Investigators will be informed of any trial-related SAEs that may warrant a change in any trial procedure. The CRO appointed by Sponsor will inform the Institutional Review Boards (IRBs)/Independent Ethics Committees (IECs) of SUSARs in accordance with local requirement, unless locally this is an obligation of the Investigator.

The Sponsor assessment of expectedness for naxitamab will be performed according to the current version of the IB. For IT and GM-CSF the applicable reference documents will be used.

10.10 Communication of Significant Safety Issues

In the event of any significant safety related issues, the Sponsor will decide upon immediate action to be taken including prompt notification of the DMC and will communicate to regulatory authorities, Investigators, IECs/IRB, and patients as needed within regulatory timelines.

10.11 Data Monitoring Committee

The DMC is an external committee composed of members whose expertise covers relevant specialties. The DMC is established to review and evaluate accumulated data from the trial with an interval between meetings of approximately 3 months and ad hoc. The DMC is established to assure patient safety and to evaluate benefit-risk balance during conduct of the trial. The DMC will provide recommendations on trial continuation, modification, or termination. Responsibilities, procedures, and workflow of the DMC are specified in the DMC charter.

Recommendation from the DMC will be discussed by the Sponsors Safety Committee. The outcome will be communicated to the regulatory authorities/IRBs/IECs/investigators if there are a significant change to trial conduct e.g., urgent safety measure, amendment to trial protocol and/or ICF.

11 LABORATORIES

11.1 Clinical Laboratory Assessments

The laboratory samples specified in [Table 9](#) will be measured by a local laboratory. Laboratory tests should be performed as described in [Table 9](#) and as clinically indicated. Please refer [Appendix 2](#) if the patient has discontinued IT treatment due to toxicity.

Table 9 Protocol required laboratory assessments

Timing of Laboratory assessments	Parameters

Screening
 
Cycle 1*: Prior to dosing D1, D5, and D8. In addition on D15
 
Subsequent cycles*: Prior to dosing D1, D5 and D8
 
EOT
 
*D10 all cycles: If modified naxitamab dosing due to missed dose (ie naxitamab to be administered on Day 12 and GM-CSF continued until Day 12)
	
Hematology
 
 • Hemoglobin • Hematocrit • White blood cells (WBC) Lymphocytes (absolute and %) • Neutrophils (absolute and %) • Eosinophils (absolute and %) • Basophils (absolute and %) • Monocytes (absolute and %) • Platelet count

Screening
 
Cycle 1: prior to dosing D1, D3, D5, D8 and D15
 
Subsequent cycles: prior to each cycle and D8
 
EOT
	
Liver and kidney function blood tests
 
 • ALT • AST • Alkaline phosphatase • Total bilirubin • Lactate dehydrogenase (LDH) • Blood urea nitrogen (BUN) • Creatinine • eGFR • Albumin (only prior to each cycle)

Screening
 
Cycle 1: prior to dosing D1, D3, D5, and D8
 
Subsequent cycles: prior to each cycle
 
EOT
	
Serum electrolytes
 
 • Sodium • Potassium • PO⁴ • Mg⁺⁺
Prior to each cycle	
Urine analysis (dipstick)
 
 • Protein • Glucose • Leucocytes

Screening
 
Prior to each cycle
 
EOT
	
Pregnancy test, if applicable
 
 • Serum pregnancy test for WOCBP see 9.2.8 for further information

The WBC and differential counts should be repeated on sequential days during all treatment cycles if ANC is $> 20 \times 10^9/L$ or WBC $> 50 \times 10^9/L$ on the day prior to GM-CSF treatment.

11.2 Immunogenicity

Samples for assessment of anti-drug antibodies (ADA) should be sent to a special laboratory for analysis. Please refer to the laboratory manual for more information.

Table 10 ADA samples

ADA assessment: Prior to dosing in each cycle EOT	
• Anti-naxitamab antibodies*
---	--

*Analyses will be performed in batches. Therefore, results will not be available during the trial

12 STATISTICAL METHODS AND DETERMINATION OF SAMPLE SIZE

12.1 General Overview

The data will be summarized in tables, as appropriate, showing the number of patients with non-missing data (n), mean, standard deviation, median, minimum, and maximum for continuous data and showing counts and percentage for categorical data. Data will also be listed as deemed appropriate.

12.2 Sample Size

With the statistical methodology for the primary endpoint (Section 12.4.1) in mind, 52 patients are needed to, with 82% power, demonstrate that the response rate is statistically significantly higher than 20%. This sample size incorporates a drop-out (here: patients either not having evaluable disease at baseline based on central review vs. local assessment, or treated patient dropping out of the trial before the first post-baseline assessment) rate of 20%, based on results from the ongoing 201 trial.

Table 11 Sample sizes, assumptions and power

Null response rate	Response rate	Unadjusted number of patients	Drop-out (20%) adjusted number of patients	Statistical Power
40%	20%	41	52	82%
40%	20%	56	70	91%
40%	25%	78	98	80%
40%	25%	102	128	90%

12.3 Populations of Interest

- Full Analysis Set

The full analysis set (FAS) will include all patients enrolled in the trial who had evaluable disease as per central review and received at least one dose of IMP.

- Per Protocol Analysis Set (PPS)

The PPS will include all FAS patients who have no major protocol violations with impact on the primary endpoint. Additional patients with other protocol violations may be uniformly excluded on the basis of data review. The precise reasons for excluding patients from the PPS will be fully defined and documented before data lock.

- Safety Analysis Set (SAF)

The SAF will include all enrolled patients who receive at least one dose of IMP.

12.4 Efficacy Analysis

Patients will be evaluated for response according to the INRC³⁷ and assigned one of the following response categories: CR, PR, MR, SD, PD or NE (Not Evaluable). In the calculations of any response rates, NE patients will be included in the denominator: not evaluable patients count as non-responders.

Overall response and DoR will be evaluated both centrally, and locally by the investigators: the central evaluation is the primary and the local evaluations are used as sensitivity analysis.

12.4.1 Primary endpoint: ORR at or before completion of four cycles

The null hypothesis: $H_0: p_{OR} = 20\%$ will be tested, using the two-sided exact binomial test, against the alternative $H_{alt}: p_{OR} \neq 20\%$ on the overall 5% significance level, where p_{OR} denotes the ORR at or before completion of four cycles. This 20% threshold is based on the results from the phase 2 study by Bagatell et al.¹⁸ in patients with primary refractory or first relapsed NB, where the ORRs to IT treatment ranged from 11% to 19%¹⁸ (see Section 4.3.3).

The ORR and rates of the response categories will be summarized in tables for the FAS and PPS. The rates will be presented with their corresponding exact binomial two-sided 95% confidence intervals.

The results will be presented for both central and local evaluation; the former is the basis for the primary endpoint and the latter is an exploratory endpoint.

OR information for individual patients will be presented in listings.

12.4.2 ORR after 2 cycles, CR rate after 2 and 4 cycles, MR rate and “MR or better” rate

The ORR after 2 cycles, CR rate at or before completion of four cycles, CR rate after 2 cycles, MR rate at or before completion of four cycles as well as the “MR or better” rate at or before completion of four cycles will be calculated and presented in the same way as the primary endpoint, see Section 12.4.1 above.

12.4.3 Duration of response

The DoR, in patients with OR, will be estimated and summarized using Kaplan-Meier methodology. If no progression or death event is observed, DoR will be censored at the time of the last response assessment. The DoR will be censored if:

- more than one assessment visit in a row is missed, or
- an anti-cancer therapy other than naxitamab and IT is administered (ignoring allowed therapies and procedures such as radiotherapy or surgery of the primary site, cf. Section 8.4.7 for details).

The distribution of the DoR will be summarized by estimates and two-sided 95% confidence intervals of the first, second and third quartiles. The number of patients with events and the number of censored patients will be presented. The reasons for censorings will be summarized.

Summary tables will be presented for the FAS and PPS. The DoR will be presented in patient data listings including the onset of response date, observed event date, censoring flag, censoring date and censoring reason. The results will be presented for both central and local evaluation. The latter will be considered exploratory.

12.4.4 Rate of patients who obtain CR in BM and convert to MRD negative

The proportion of patients with disease in BM at enrollment who obtain CR in BM and convert to MRD negative at or before completion of four cycles will be analyzed and

presented in the same way the primary endpoint for the sub-population of patients who are BM MRD positive at baseline, for the FAS and PPS.

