6.2 Secondary Endpoints

1. ORR after 2 cycles defined as the proportion of patients obtaining a centrally assessed CR or PR according to the INRC at completion of two treatment cycles
2. Duration of response (DoR), defined as the time from first centrally assessed OR (CR or PR according to the INRC) to PD or death
3. CR rate, defined as the proportion of patients obtaining a centrally assessed CR according to the INRC at or before completion of four treatment cycles
4. CR rate after two cycles defined as the proportion of patients obtaining a centrally assessed CR according to the INRC at completion of two treatment cycles
5. Minor response (MR) rate, defined as the proportion of patients obtaining a centrally assessed MR according to the INRC at or before completion of four treatment cycles
6. "MR or better" rate, defined as the proportion of patients obtaining a centrally assessed CR, PR or MR according to the INRC at or before completion of four treatment cycles
7. Proportion of patients with disease in BM at enrollment who obtain centrally assessed CR in BM and convert to minimal residual disease (MRD) negative (assessed by reverse transcriptase-quantitative polymerase chain reaction (RTqPCR)) at or before completion of four cycles
8. Time to First Subsequent Therapy or death (defined as the time from initiation of treatment with investigational medicinal products (IMP) until death or start of new anti-cancer treatment (prohibited as per protocol))
9. PFS defined as the time from first IMP administration until centrally assessed PD or death, whichever comes first
10. OS defined as the time from first IMP administration until death
11. 1- and 2-years PFS defined as the proportion of patients alive and with no centrally assessed PD at 1- and 2 year, respectively after first IMP administration
12. 1- and 2-year OS defined as the proportion of patients alive at 1- and 2 years after first IMP administration
13. Safety incl. incidence of AEs and SAEs graded according to Common Terminology Criteria for AEs (CTCAE) version 5.0
14. Pain during naxitamab infusions as assessed by Wong Baker- and FLACC scales
15. Incidence of ADA (including assessment for neutralizing potential and time to first positive ADA assessment from first day of naxitamab administration)
16. Number of naxitamab infusions done in an out-patient setting defined as infusions not requiring admission to hospital due to adverse events

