9 PROCEDURES AND ASSESSMENTS

9.1 Efficacy Assessments

9.1.1 Response Assessments

The primary endpoint is ORR. This will be based on BM biopsies and aspirates (histology, cytology) and imaging and assessed according to INRC³⁷ (see [Table 5](#), [Table 6](#), [Table 7](#) and [Table 8](#)). The imaging should be done either as:

- CT/MRI and ^{123}I -MIBG + single-photon emission computed tomography (SPECT)/CT **or**
- CT/MRI and ^{123}I -MIBG whole body planar scan if no hybrid gamma camera is available **or**
- CT/MRI and FDG-PET/CT if MIBG-nonavid tumor

The same imaging modality should preferably be used throughout the trial (please refer to the imaging acquisition guideline).

BM examinations should comprise bilateral BM trephine biopsies and BM aspirates (i.e., 2+2 samples) as per INRC⁴³ (please refer to laboratory manual).

BM trephine biopsies should be evaluated by histology and immunohistochemistry (IHC). Two highly specific target antigens should be used for IHC, such as synaptophysin, tyrosine hydroxylase, chromogranin A, or paired-like homeobox 2b (PHOX2B). The target antigens used for IHC should remain the same throughout the trial. BM aspirates should be evaluated by cytology and MRD (please see [Section 9.1.1.1](#)). If volume of aspirates is not sufficient, BM response assessment should be prioritized over MRD assessment by RTqPCR.

Images and BM biopsies/aspirates (excluding results from RTqPCR, see [Section 9.1.1.1](#)) will be assessed locally at site but will also be reviewed centrally by independent external experts. The local response assessment will be used throughout the trial for the decision to continue or discontinue IMPs. Imaging and BM biopsies/aspirates must be done within 7 days (+ 3 days) of the same response assessment (except at screening). The centralized review will be done retrospectively.

Table 5 Primary (soft tissue) Tumor response

Response	Anatomic + MIBG (FDG-PET [†]) Imaging	
CR	< 10 mm residual soft tissue at primary site AND Complete resolution of MIBG or FDG-PET uptake (for MIBG-nonavid tumors) at primary site	
PR	$\geq 30\%$ decrease in longest diameter of primary site AND MIBG or FDG-PET uptake at primary site stable, improved, or resolved	
PD	$> 20\%$ increase in longest diameter taking as reference the smallest sum on study (this includes the baseline sum if that is the smallest on study) AND Minimum absolute increase of 5 mm in longest dimension [‡]	

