9.1.2 Timing of response assessment

For timing of response assessment for patients who have discontinued IT treatment due to toxicity, please refer to [Appendix 2](#).

The response assessments will be performed after C2, C4, C8, C13, and EOT. All response assessments (except EOT) should be performed before D1 of next cycle.

In addition, for patients who achieve:

- a first CR or PR after C4 *OR*
- a first CR or PR after C8

a confirmatory response assessment should be performed within 4-6 weeks after detection of the overall response.

If the patient discontinue treatment due to PD, response assessment at EOT is not required provided that PD is documented by scan and/or biopsy.

For patients who have not experienced PD or started new anti-cancer treatment, response assessment should be performed at approximately every 4 months after EOT during long-term FU (see Section [3](#)).

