12.4.6 PFS and OS

PFS will be censored in the same way as DoR. If no death event is observed, OS will be censored at the date of the last assessment. PFS and OS will be estimated using Kaplan-Meier methods and presented in same way as DoR. In addition, the Kaplan-Meier estimates of the proportions, together with the corresponding CIs, of patients without progression or death (PFS) and alive (OS) at 1 and 2 years will be presented for the two endpoints respectively. The PFS results will be presented for both central and local evaluation. The latter will be considered exploratory.

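### Central PFS and DoR are censored at new anti-cancer therapy and after consecutive missed visits, and no PFS or DoR analysis in the protocol relaxes these two rules, although the censoring is likely informative

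*Combined protocol and SAP*

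**What the plan says.** **Definition.** Section 6.2 (no. 9) gives "PFS defined as the time from first IMP administration until centrally assessed PD or death, whichever comes first". No. 11 defines 1- and 2-year PFS in the same terms, and no. 2 ends DoR at PD or death. None of them makes an exception for new therapy or missed visits.

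**Analysis.** Section 12.4.3 has a default rule, "If no progression or death event is observed, DoR will be censored at the time of the last response assessment", and two further triggers: "more than one assessment visit in a row is missed, or" and "an anti-cancer therapy other than naxitamab and IT is administered" (permitted local treatments are ignored). It gives no censoring date for either trigger. It also does not say what happens if the patient later dies or returns without progression. Section 12.4.6 adds "PFS will be censored in the same way as DoR".

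**Who calls PD, and what follows.** Section 9.1.1 states "The local response assessment will be used throughout the trial for the decision to continue or discontinue IMPs" and also "The centralized review will be done retrospectively". PD ends all IMPs (Section 7.12, general criterion 12). The end-of-treatment assessment is waived once PD is documented by scan or biopsy. Follow-up imaging is then limited by Section 9.1.2: "For patients who have not experienced PD or started new anti-cancer treatment, response assessment should be performed at approximately every 4 months". Section 7.8 and flow-chart footnote 14 limit it by PD alone.

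**Related analyses.** DoR, PFS and 1- and 2-year PFS are also planned on local assessment (Section 6.3 no. 5, Sections 12.4, 12.4.3 and 12.4.6). Time to first subsequent therapy (TFST) and OS are separate endpoints. Section 12.4.3 already plans a summary of the reasons for censoring.

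**The concern.** Kaplan-Meier estimation treats a censored patient as having the same outlook as those still at risk. A patient who stops for local PD, moves to another therapy or misses consecutive assessments plausibly has a worse one. Definition and analysis also part company: a patient who starts new therapy and then dies is an event under Section 6.2 but censored under Sections 12.4.3 and 12.4.6.

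The synopsis lists DoR, PFS and 1- and 2-year PFS as key secondary endpoints. In a single-arm trial there is no control group in which a distortion of this kind could offset itself. The gap involved can be long. With follow-up visits about 4 months apart, two missed visits leave 3 × 4 = 12 months between attended assessments, while the historical median PFS quoted in Section 4.1 is 6.4 months.

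**Working it through.** **Step 1: the plan's own figures.** No design figure is stated for PFS or DoR. The only one is for ORR (Section 12.2), and it reproduces: with n = 41, rejecting at 14 or more responses has upper-tail alpha 0.0242 and power 0.822, and 41/0.8 rounds up to 52. It does not bear on this point.

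**Step 2: how each course of events is counted.**

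| Course | Central PFS/DoR | Local PFS/DoR | Elsewhere |
|---|---|---|---|
| Local PD, confirmed centrally | Event | Event | – |
| Local PD, not confirmed, then new therapy | Censored; a later death is not counted | Event | TFST event |
| Local PD, not confirmed, no new therapy, then death | Can still be an event at death | Event at PD | TFST (by definition) and OS event |
| No PD, new therapy, then death | Censored | Censored | TFST and OS event |
| Two or more visits missed, then death | Unclear: event by 6.2, censored on one reading of 12.4.3 | Unclear | TFST (by definition) and OS event |
| Two or more visits missed, then seen progression-free | Unclear whether follow-up resumes | Unclear | – |

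TFST does not count PD, and it runs from first treatment, so it cannot stand in for DoR. Its analysis text (Section 12.4.5) does not repeat that death is an event, although Section 6.2 does. OS does not measure progression. So no PFS or DoR analysis in the protocol counts new therapy as an event, and none clearly counts death after missed visits.

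**Step 3: illustration of size.** Inputs:
- True 1-year PFS of 37%, from the compassionate-use series in Section 4.3.4, or 21%, from the historical meta-analysis in Section 4.1.
- A fraction f of true progressions recorded as censorings. The documents give no value, so 10% to 30% is an assumption.
- Constant hazard.

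For 37%, the hazard is −ln(0.37) = 0.994 per year. If a fraction f of events is censored at the event time, the Kaplan-Meier estimate tends to S(t)^(1−f), and the median to 12 × ln 2 / (0.994 × (1−f)) months. For f = 20%, 0.37^0.8 = 0.451 and 12 × 0.693 / (0.994 × 0.8) = 10.5 months.

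| f | 1-year PFS, true 37% | Median (months), true 37% | 1-year PFS, true 21% |
|---|---|---|---|
| 0 | 37.0% | 8.4 | 21.0% |
| 10% | 40.9% | 9.3 | 24.5% |
| 20% | 45.1% | 10.5 | 28.7% |
| 30% | 49.9% | 12.0 | 33.5% |

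**Step 4: check with scheduled visits.** A simulation used 42 patients, 1,500 runs, and assessments at weeks 6, 12, 24, 39 and 45, then about every 4 months. For the 37% case, counting all events gives about 42%, because progression is recorded only at the next visit. Censoring them gives 46–47% (f = 10%), 50–51% (20%) and 54–56% (30%). The direction is the same.

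**Step 5: in patients.** With 41 evaluable patients, a 1-year PFS of 37% implies 41 × 0.63 ≈ 26 events in the first year. Twenty per cent of these is about five patients.

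**The case against.** A reader might infer that no planned analysis counts any of these outcomes as an event, and that both estimates are therefore shown to be biased upward. The documents do not support that. Local PD is an event in the planned local DoR and PFS, new therapy or death is the TFST event, and every death is an OS event. What remains is narrower: the local analyses carry the same two censoring rules, and TFST and OS answer other questions.

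Nor can it be said that deaths after missed visits are dropped. Section 12.4.3 does not settle whether the rule overrides a later death, and Section 6.2 counts death. That is an ambiguity, which itself needs resolving.

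Other objections have weight:
- **Direction.** A local PD that central review rejects may not be a true progression, and central review may date PD earlier than the site did, which shortens central PFS. Upward bias is the likely direction, not a demonstrated one.
- **Safeguard.** Section 7.8 calls for the end-of-treatment visit before new therapy starts, so a switching patient should have documented PD or a fresh assessment. This reduces unobserved progression. It does not help where central review does not confirm PD, and it does not restore a later death.
- **Size.** The 37% comes from a heavily pretreated series with a 95% CI of 21.8% to 62.9%, and every shifted value lies inside it.
- **Stakes.** PFS and DoR are descriptive. No test, threshold or formal historical comparison is planned for them.
- **Absence.** Section 12.13 leaves further detail to a SAP. The supplied text holds the protocol's statistical section but no separate SAP, so the gap is asserted for the protocol only.

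**Conclusion.** The point holds in its limited form. The two censoring rules depart from the Section 6.2 definition and are plausibly informative, and no PFS or DoR analysis in the protocol relaxes them. Local PD is covered only by the exploratory local analyses.

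The likely effect is to raise central PFS and DoR. The rise of 4 to 13 percentage points in 1-year PFS (37% to 41–50%) is an illustration. It rests on an assumed 10% to 30% of progressions censored, a constant hazard, and every such case being a true progression. The actual amount cannot be derived from the documents. The primary ORR analysis is unaffected. A change is worth making because it is cheap and these are key secondary endpoints of a single-arm trial.

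**What to change.** 1. **Narrow and complete the missed-visit rule in the main analysis.** Apply it only when PD or death is first documented immediately after two or more consecutive missed visits. State that censoring is then at the last adequate assessment before the gap, and that a later progression-free assessment closes the gap.
2. **Prespecify one sensitivity analysis each for central PFS and central DoR.** The event is the earliest of central PD, local PD that ended assessment, start of new anti-cancer therapy, or death at any time. There is no censoring for missed visits.

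The cost is wording and one extra Kaplan-Meier table per endpoint. Deaths, PD and new anti-cancer therapy are already collected through follow-up (Section 7.8 and flow-chart footnote 5). The added estimates will be less favourable, and some switches for toxicity or by choice will count as events. They should therefore be presented as a conservative bound beside the main analysis, not as its replacement.
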